13. STATISTICAL CONSIDERATIONS

13.6. Overview

Detailed description of the plan for statistical analysis of each endpoint will be detailed in a Statistical Analysis Plan (SAP) that will be prepared after the final study protocol is approved. The SAP will be prepared by the DCC senior statistician under [name] supervision.

Descriptive statistics will be used to summarize patient socio-demographic and clinical characteristics. The analyses of primary and secondary outcomes as well as the summary description of pain-related side effects and safety will be carried out by the DCC statistical service. Means, standard deviations, medians, 25th and 75th percentiles, minimum and maximum will be presented for continuous variables; the number and frequency of patients in each category will be presented for nominal variables. For all analyses, a two-sided p-value ≤ 0.05 will be considered statistically significant. Analyses will be performed using SAS version 9.4 or higher software (SAS Institute, Inc., Cary, NC).

Multiple Comparisons: With the pre-specified primary and secondary analyses, we

recognize that there is a multiplicity of analyses to be performed, which leads to an increased probability that at least one of the comparisons could be "significant" by chance. There are adjustments (e.g., based on the Bonferroni inequality) that can be used to preserve the overall type I error level. To attempt to adjust for the effects of the repeated significance testing that will occur as part of potential interim monitoring (discussed below), plus to adjust for the multiplicity of secondary outcomes, would require that very small significance levels be used for every comparison. Rather than taking this approach we will be conservative in the interpretation of secondary analyses, taking into account the degree of significance, and looking for consistency across outcomes. The actual p-value for each comparison will be reported to aid in the overall interpretation. In addition to the pre-specified primary outcome, we will use pre-specified secondary outcomes and pre-specified subgroups to help avoid over-interpretation and to help guard against and reduce the problems inherent with multiple testing.

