13.8. Analysis of Primary Endpoint

The statistical comparison of the two randomized arms with respect to the primary outcome is comparing the means of the pain score reductions between the two arms. A comparison between two groups will be performed, adjusting for the initial pain score at ED time of placement in a treatment area, biological variables of SCD genotype, age and gender. This analysis will utilize linear regression with pain score reduction as the dependent variable and treatment indicator with pain score at time of placement in a treatment area as covariates (independent variables). Rejection of the null hypothesis stating that coefficient for the treatment indicator is zero will provide evidence for presence of the treatment effect. This comparison will utilize subjects with available measure of the primary outcome. In addition to the statistical hypothesis testing, 95% confidence intervals descriptively summarizing the difference in outcome between the two arms, as well as outcome in each arm will be computed.

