Missing Data: Because the outcome data are collected during an ED visit over a time period up to 6 hours, we don't expect missing data due to any subject deaths during this time or withdrawal from the study. However, the pain score reduction may be missing if the pain score at the beginning or the end is not recorded (e.g., if patient left without doing the interview prior to discharge or hospital admission). We will make every effort to prevent missing data on pain score at the beginning and document reasons for missing pain score at final disposition (discharge or admission). If more than 5% of randomized patients have the pain score reduction missing, we will use multiple imputations in the primary analysis to mitigate potential bias of the complete case analysis. This analysis is valid under the missing at random (MAR) assumption. First, an imputation model via linear regression will be developed (based on available data) relating the pain score reduction with a collection of covariates including initial pain score, treatment indicator, baseline characteristics, and possible interactions of covariates with treatment. A total of 1000 data sets with imputations of pain score reduction utilizing the imputation model will be generated. Each of such data sets will be analyzed with linear regression (as described above), and the combined results comparing two groups will be reported by taking into account of variability due to multiple imputations.

Sensitivity analysis: Unfortunately, the MAR assumption cannot be verified with the observed data alone and we will consider sensitivity analysis to examine impact of departure from the MAR assumptions on the treatment effect. We will consider the best and worst scenarios where the worst scenario is to impute the pain score reduction to be zero for patient-specific analgesic protocol and observed maximum pain reduction for the weight-based analgesic protocol and the reverse is used for the best scenario.

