4. ENDPOINTS

4.1. Primary Endpoint and Hypothesis

The Primary Endpoint of the study population is the change in pain scores from the time of placement in a treatment area to the time of disposition (hospital admission, discharged home, assigned to observation status) or a maximum treatment duration of 6 hours, whichever comes first.

The Primary Hypothesis of the study population is that the patient-specific analgesic protocol is superior to the weight-based analgesic protocol. (section 11 of the protocol). The sample size of 230 subjects with ED visits provides 90% power to detect 14-mm clinically significant assumptions of the same standard deviations (SD) of 31 mm in pain score reductions in the two groups while accounting for 10% missing data rate.

Method of the Final Analysis will be linear regression used to test the primary hypothesis with pain score reduction (0-100mm) as the dependent variable and treatment indicator with pain score at arrival, biological variables of SCD genotype, age and gender as covariates (independent variables). The primary analysis for hypothesis-testing will be done on the observed data without imputation and without regard to the proportion of missing cases. Summaries of the p-value, 95% confidence intervals and the difference in outcome between the two arms, as well as outcome in each arm will also be computed and presented in tabular and graphic format.

Details will be presented later (section 7 of the SAP).

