Missing Data and Sensitivity Analyses of the Primary Endpoint: If more than 5% of randomized patients have the pain score reduction missing, we will use multiple imputations in a **sensitivity analysis**, which would be considered supportive if it gave results consistent in direction and magnitude with the primary analysis. Highly inconsistent results would require further review of how and why the data were missing and suggest concerns with study conduct. This analysis is valid under the missing at random (MAR) assumption. First, an imputation model via linear regression will be developed (based on available data) relating the pain score reduction with a collection of covariates including initial pain score, treatment indicator, baseline characteristics, and possible interactions of covariates with treatment. A total of 1000 data sets with imputations of pain score reduction utilizing the imputation model will be generated. Each of such data sets will be analyzed with linear regression (as described above), and the combined results comparing two groups will be reported by taking into account of variability due to multiple imputations. In **another potential sensitivity analysis**, we will also consider the best and worst scenarios where the worst scenario is to impute the pain score reduction to be zero for patient-specific analgesic protocol and observed maximum pain reduction for the weight-based analgesic protocol and the reverse is used for the best scenario. (section 13.8. of the protocol)

If fewer than 5% of patients have a missing arrival or discharge pain score evaluation, we will perform the primary analysis on the patients without missing data. Two sensitivity analyses will be done:

- 1.) Worst case, assuming missing discharge pain scores are 0 in the weight-based arm and 100 in the patient-specific arm. Missing arrival scores will be assigned the mean of the study population arrival scores.
- 2.) LOCF – imputing missing discharge scores as the last score recorded on the Q 30-minute assessment prior to discharge. Missing arrival scores will be assumed to take the value of the first score recorded on the Q 30-minute assessment. {Although LOCF is in general not a recommended technique, it could be informative in this situation.} The missingness would be due to lack of assessment resulting from one of the four reasons below, each of which could be informed by the most recent pain score.
 - i. The patient is discharged home

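### Above 5% missing, Protocol 13.8 makes multiple imputation primary while SAP 4.1 keeps observed data primary; the 5% denominator is unclear and the imputation model does not name the half-hourly pain scores

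*SAP*

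**What the plan says.** Protocol 13.8 first describes a regression on patients who have the outcome: "This comparison will utilize subjects with available measure of the primary outcome". Its missing-data paragraph then changes the rule. The trigger reads "If more than 5% of randomized patients have the pain score reduction missing". Once it is met, the protocol's commitment is "we will use multiple imputations in the primary analysis to mitigate potential bias of the complete case analysis".

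SAP 4.1 states the opposite for the hypothesis test: "The primary analysis for hypothesis-testing will be done on the observed data without imputation and without regard to the proportion of missing cases". It then repeats the protocol's trigger, but makes multiple imputation (MI) a sensitivity analysis that counts as supportive if it agrees with the primary result. It cites Protocol 13.8 as the source. Best- and worst-case imputation is described there as a further potential sensitivity analysis.

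A second tier of SAP 4.1 opens "If fewer than 5% of patients have a missing arrival or discharge pain score evaluation" and continues "we will perform the primary analysis on the patients without missing data". It adds a worst case and a last-observation-carried-forward (LOCF) analysis from the half-hourly scores. The SAP defends LOCF by saying that the latest pain score may bear on each reason for a missing final score.

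The MI model in both documents uses "a collection of covariates including initial pain score, treatment indicator, baseline characteristics, and possible interactions of covariates with treatment". SAP 7.1 analyses the primary endpoint in the modified-ITT population and defines baseline as before placement in the treatment area. Protocol 13.6 leaves the detailed analysis plan to the SAP.

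**The concern.** There are three linked faults and one minor gap.

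- **Two primary analyses.** Above 5% missing, the documents name different primary analyses, and the trial's own planning rates lie above 5%. If the choice is settled only after the data are seen, the primary result is not fully pre-specified.
- **Unclear trigger.** The upper tier counts randomized patients, the lower tier counts patients, and the analysis set is about half of those randomized. Under the protocol the denominator decides the primary analysis. Under the SAP it decides only which sensitivity analyses run.
- **A weak check.** The half-hourly scores are not baseline by the SAP's definition and are not named in the MI model. The SAP uses the latest score only for LOCF, and only below 5%. If missing final scores depend on pain during the visit, MI from the named covariates would not show it, and its agreement with the observed-data result would be read as reassurance.
- **Minor gap.** The MI tier does not say how a missing initial score is handled. The lower tier does.

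**Working it through.** **1. The plan's own figure.** Inputs from Protocol 13.7: 230 patients, 10% missing, difference 14 mm, SD 31 mm, two-sided 0.05. Evaluable patients: 230 × 0.9 = 207, or 103.5 per arm. Standard error: 31 × √(2/103.5) = 4.31 mm. Then 14/4.31 − 1.96 = 1.29, which gives power 90.1% (89.9% by the noncentral t). The stated 90% reproduces, and this point does not affect it.

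**2. Does the conflict arise?** The planned rate is 10%: 0.10 × 230 = 23 missing. In the R34 pilot, 48 of 52 had the outcome, so 4/52 = 7.7% (reported as 8%), or about 18 of 230. Both exceed 5% of 230.

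**3. The trigger.** 0.05 × 230 = 11.5, so MI starts at 12 missing. 0.05 × 460 = 23, so MI starts at 24.

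| Missing | Share of 230 | Share of 460 |
|---|---|---|
| 12 | 5.2% | 2.6% |
| 18 (R34 rate) | 7.8% | 3.9% |
| 23 (planned rate) | 10.0% | 5.0% |
| 24 | 10.4% | 5.2% |

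The 460 column counts patients with no ED visit as not missing. If they count as missing, the rate is at least 230/460 = 50% and MI always applies. Exactly 5% falls in neither SAP tier. It cannot occur at 230, but on 460 it is the planned number.

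**4. Why MI adds little.** Filling a missing outcome from a regression on treatment and baseline covariates, then refitting nearly the same regression, returns nearly the same treatment coefficient. Patients without the outcome add information only through variables outside the analysis model.

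**5. Simulation (assumed mechanisms).** There were 600 trials per scenario, 30 imputations and 230 patients, with 10% missing. Mean reductions were 43 and 29 mm (true difference 14) and the SD was 31. The initial score was 85 (SD 10). The last half-hourly score correlated 0.6, 0.84 or 0.95 with the final score. The analysis model had treatment, initial score, age, gender and genotype. The MI model added one prognostic baseline variable and two treatment interactions. Monte Carlo standard error was about 0.17 mm. Estimates in mm at correlation 0.84, with dependence on the last score in logits per SD:

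| Missingness | Observed | MI, named covariates | MI plus last score |
|---|---|---|---|
| Non-informative | 14.0 | 14.0 | 13.9 |
| Both arms, +1 | 13.4 | 13.4 | 14.0 |
| Both arms, −1 | 13.8 | 13.8 | 14.4 |
| Patient-specific arm only, +1 | 16.5 | 16.4 | 14.2 |
| Weight-based arm only, +1 | 11.4 | 11.5 | 14.1 |

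Across all three correlations, the observed-data estimate was:

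- 13.8–14.1 with non-informative missingness;
- 13.5–14.4 with the same dependence in both arms at 0.5 logit, and 13.0–13.9 at 1 logit;
- 11.0–12.2 or 15.6–16.9, by direction, with one-arm dependence at 1 logit;
- 11.0–12.2 or 15.8–16.7 with opposite dependence by arm at 0.5 logit, and 8.8–10.9 or 17.1–19.0 at 1 logit.

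MI from the named covariates stayed within 0.3 mm of the observed-data estimate throughout. MI with the last score gave 13.6–14.4. The two rules disagreed on significance in 0%–4.2% of trials. With scores bounded to 0–100 (true difference 12.3–12.8), same-dependence estimates were 12.0–12.6, arm-differing estimates 8.5–17.0, and MI with the last score 12.1–12.9.

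A second simulation used correlation 0.8, 8–15% missing, and a steeper 1.5-logit slope for opposite dependence. Observed data and baseline-only MI agreed within 0.01 mm. Both were 0.6–0.9 mm low under the same dependence (1 logit) and about 5–9 mm high under opposite dependence. Adding the last score came within 0.1 mm of the full-data estimate.

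**6. The planned bounds.** With non-informative 10% missing per arm and an assumed maximum reduction M of 85 to 100 mm:

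- worst case = 0.9 × 43 − (0.9 × 29 + 0.1 × M) = 12.6 − 0.1M = 4.1 to 2.6 mm;
- best case = 12.6 + 0.1M = 21.1 to 22.6 mm.

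The bounds contain the true 14 mm but span 17 to 20 mm.

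**The case against.** The strongest reply is that little doubt remains about what will be run. The protocol hands the detailed plan to a later SAP, the SAP's rule is categorical, and it agrees with the protocol's own opening statement about available outcomes. This is largely fair: an analyst following the SAP has a rule. But demoting MI reverses a stated protocol rule rather than filling in detail, and no text gives the SAP precedence. Pages are missing from the public copies, so the absence of a reason can be asserted only of the visible text.

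The lower-tier sentence does not strictly contradict the SAP's general rule, since it applies the same analysis. It is only poorly worded. The 460 reading is strained, because the outcome exists only for patients with a recorded visit and the planning rates use that base. Still, the literal wording refers to randomized patients.

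The covariate list is open, so the half-hourly scores are not excluded. The bias sizes rest on assumed mechanisms, and the two simulations differ in size because their inputs differ. No passage suggests arm-differing missingness, and blinding of patients and assessors makes it less likely. With the same dependence in both arms, the bias is about 1 mm or less. In one scenario, adding the last score gave 14.4 mm, farther from 14 than the observed-data 13.8.

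SAP 4.1 also has safeguards: each center must explain its first missing score and plan prevention, and highly inconsistent results prompt a review of the missingness. These reduce the risk but do not reconcile the two rules. The review step depends on MI disagreeing with the primary result, which the named model seldom allows.

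**Conclusion.** The concern holds and should be fixed. The text conflict is certain and falls at the trial's planned missing rate. It is mainly a fault of pre-specification: the two rules gave nearly equal estimates and disagreed on significance in at most 4.2% of simulated trials. The stated power is unaffected.

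The denominator moves the trigger from 12 to 24 missing patients if all 460 randomized are counted. The MI check as named has little power to reveal dependence on in-visit pain. Under assumed one-arm dependence of 1 logit per SD, the estimate moved about 2 to 3 mm in either direction, and MI moved with it. Those sizes illustrate the mechanism and are not predictions. The planned bounds are too wide to show a shift of that order.

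**What to change.** - State one primary missing-data rule in both documents, for example by amending Protocol 13.8 to the SAP rule and giving the reason.
- Reword the SAP's lower-tier sentence so that it does not appear to make the primary analysis conditional on the missing rate.
- Define the trigger as the proportion of modified-ITT patients with a missing reduction, with tiers of more than 5% and 5% or less.
- Name the half-hourly pain scores as auxiliary variables in the MI model. Impute the placement and final scores and derive the reduction from them, which also covers missing initial scores.
- Keep the best- and worst-case bounds and commit to running them. A delta-adjusted tipping-point analysis is optional.

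The cost is wording in Protocol 13.8 and SAP 4.1 plus some programming. The half-hourly scores are already collected, so no new data are needed.

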The previous R34 study indicated that 49% of the subjects had at the ED visit over the 13 months of enrollment. The observed missing data rate in pain score reduction is 8%, due to either missing pain score at arrival or at discharge. No enrolled patient died in the previous R34 study. The overall SD of the pain score reduction from arrival to discharge was 30, with 27 and 31 in the weight-based and patient-specific analgesic protocol groups, respectively. Therefore, our assumptions of 10% missing data rate and a SD=31 in pain score reduction are conservative. With a 24-month enrollment period in this study, nearly double the enrollment time in the R34 study, it is conservative to assume that 50% of the randomized subjects will have a qualifying ED visit within the 24-month enrollment period. Thus, a total target sample size of 230, with 460 randomized subjects, is a reasonable and conservative estimate. As detailed in Table 4, we varied the missing data rate from 5%-10%, the SD of pain score reduction from 30-33, and percent of randomized subjects with an ED visit from 50% to 75%. All scenarios give 85% or higher power to detect a 14-mm clinically significant difference with the target sample size of 230 in the ITT population at 0.05 level. While the R34 study didn't have sufficient power to detect a 14-mm difference, the proposed study will have 90% power to detect this difference if outcome data is similar to the R34 study. Our sample size calculation assumes the pain score reduction follows a normal distribution based on data from the R34 study that indicated that the normality assumption was not violated.

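### The multiple imputation models only the pain reduction, with the initial score as predictor, so a patient with no placement score cannot be imputed as written

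*SAP*

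**What the plan says.** SAP 12.1 defines the reduction as the placement score minus the disposition score. Protocol 13.8 accepts that "the pain score reduction may be missing if the pain score at the beginning or the end is not recorded". Protocol 13.7 reports that the 8% missing in the R34 pilot was "due to either missing pain score at arrival or at discharge".

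SAP 4.1 then sets out two branches.

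- **Above 5%.** "If more than 5% of randomized patients have the pain score reduction missing, we will use multiple imputations", here as a sensitivity analysis. The model is a linear regression "relating the pain score reduction with a collection of covariates including initial pain score, treatment indicator, baseline characteristics, and possible interactions". "A total of 1000 data sets with imputations of pain score reduction utilizing the imputation model will be generated". Each data set is analysed with the primary regression, which has the initial score as a covariate. Best and worst scenarios are also considered; these set the missing reduction itself to zero or to the observed maximum.
- **Below 5%.** "If fewer than 5% of patients have a missing arrival or discharge pain score evaluation", complete patients are analysed and two sensitivity analyses follow. In the worst-case one, "Missing arrival scores will be assigned the mean of the study population arrival scores". In the last-observation-carried-forward (LOCF) one, "Missing arrival scores will be assumed to take the value of the first score recorded on the Q 30-minute assessment".

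Under the SAP, the primary test uses observed data whatever the missing rate. Protocol 13.8 describes the same imputation model but makes it part of the primary analysis. Neither document gives a model for the initial score or names a joint or chained method.

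**The concern.** The plan foresees two ways of losing the outcome, and its imputation model can deal with only one of them. A regression returns no value for a patient whose predictor is blank, and the analysis model then asks for the same blank value again.

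What is at stake is how the sensitivity analysis can be read. SAP 4.1 treats agreement with the primary result as support, and strong disagreement as a reason to look into trial conduct. If one class of missing patients never enters the analysis, agreement says nothing about that class. The gap would weigh more under protocol 13.8, where the imputation belongs to the primary analysis.

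A separate and smaller matter lies in the below-5% branch. The 30-minute series begins after placement (SAP table 16.1 runs from 30 to 360 minutes), so its first score can follow the first opioid dose. If pain has already fallen by then, using that score as baseline makes the reduction look smaller than it was.

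**Working it through.** **1. The plan's own figure.** Inputs from protocol 13.7: 230 patients, 10% missing, SD 31 mm, difference 14 mm, two-sided 0.05, 1:1 allocation.

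- Per arm: 230 × 0.90 / 2 = 103.5.
- Standard error: 31 × √(2/103.5) = 4.31 mm.
- Power: Φ(14/4.31 − 1.96) = 0.901 (0.899 by the noncentral t). The stated 90% reproduces.

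**2. Who can be imputed.** Write P for placement score, D for disposition score, R = P − D.

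| Missing | Predictor P | Imputed R | In the analysis regression |
|---|---|---|---|
| D only | known | yes | yes |
| P only | blank | no | no, although D is recorded |
| both | blank | no | no |

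A check on made-up data with 23 of 230 reductions missing, 12 for lack of P and 11 for lack of D, gave a prediction for 11 and none for 12.

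**3. Why the unused D matters.** If R = a + βT + γP, then −D = a + βT + (γ − 1)P, with the same β. In the baseline-adjusted model D therefore carries the outcome information, and the described imputation discards it for patients lacking only P. Software that also filled in P would not fully cure this. Imputed P minus separately imputed R need not equal the recorded D.

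**4. How many patients.** 0.10 × 230 = 23 missing. The split by cause is not given, so the range is 0% to 100%.

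| Share lacking P | Not imputed | N after imputation | Power, upper bound |
|---|---|---|---|
| 0% | 0 | 230 | 93% |
| 25% | 6 | 224 | 92% |
| 50% | 12 | 218 | 92% |
| 75% | 17 | 213 | 91% |
| 100% | 23 | 207 | 90% |

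The power column treats imputed patients as fully observed, so it is only a bound. Even the last row is the 207 that the design already assumed.

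**5. Which branch is likely.** The pilot rate was 4/52 = 8% and the planning rate is 10%. Both exceed 5% if the trigger is read against the 230 with an ED visit. Read literally against 460 randomized patients, 23/460 is exactly 5%, which falls in neither branch.

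**6. Size of the first-30-minute effect.** Assume 11 of 230 (about 5%) lack P. As an extreme, assume the whole 14 mm arm difference is already present at 30 minutes.

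- Unadjusted: 11/230 × 14 = 0.67 mm too small.
- Adjusted: the substituted P acts only through its covariate. With an assumed slope γ = 0.5, the shift is (1 − 0.5) × 0.67 = 0.33 mm. It is 0.67 mm at γ = 0 and nil at γ = 1.
- A simulation (assumed placement mean 85, SD 12, γ = 0.5, residual SD 30) gave 13.97 mm on full data, 13.68 adjusted and 13.30 unadjusted, against a standard error of about 4 mm. Under the mean rule the adjusted estimate stayed at 13.97.

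**The case against.** The strongest reply is that little hangs on this. The SAP's primary test ignores imputation altogether. Patients and research assistants are blinded to arm, so loss of the placement score is not obviously related to treatment, and dropping such patients would then mainly cost precision. In the simulation above, dropping 23 at random left the estimate at 13.98 mm and raised the standard error from 3.97 to 4.20. One sentence on how a missing initial score is imputed might be enough. All of this stands as an argument about size. It does not make the described model able to impute these patients.

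Four stronger readings are tempting, and the documents do not support them.

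- *The whole missing-data plan covers only one cause.* It does not follow. The best and worst scenarios impute the reduction whichever score is missing and can feed the unadjusted t-test of SAP 7.7.1; only the adjusted regression still needs the initial score.
- *The mean and the first 30-minute score are fallbacks for the imputation.* They belong to the below-5% branch. Above 5% no rule for a missing initial score is stated.
- *Assigning the mean spoils the worst-case analysis.* The extreme values there apply to discharge scores. The mean is a neutral companion rule, so this is mostly a question of label.
- *The first-30-minute rule biases the result against the patient-specific arm.* That needs larger starting doses and a larger early fall in that arm. Protocol 8.2.1 makes this plausible, because a prior ED dose below the weight-based dose is replaced by the weight-based dose. The documents give no distribution of starting doses by arm.

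**Conclusion.** The point holds as a modest correction to the missing-data analysis. The imputation in SAP 4.1 and protocol 13.8 leaves out every patient without a placement score, and any disposition score recorded for that patient goes unused. At 10% missing this means 0 to 23 of 230 patients. A reader might infer that the primary result or the sample size is in doubt. Under the SAP neither is, because the primary test uses observed data and the 90% power already allows for losing all 23. The gap would bear on the primary result only if protocol 13.8 were followed on the role of the imputation.

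The first-30-minute rule is a lesser issue. Under extreme assumptions it costs about 0.7 mm in the unadjusted comparison and about 0.3 mm in the adjusted one.

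The conclusion rests on reading the text as a single regression, as written, and on taking the initial or arrival score in SAP 4.1 to be the placement score. The slope, the early pain fall and the split of causes are assumptions.

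**What to change.** In SAP 4.1 and protocol 13.8, impute the placement and disposition scores themselves by chained equations, each predicting the other, with treatment, its interactions and the baseline characteristics in the models. In each completed data set, derive both the reduction and the baseline covariate from the two scores. A recorded disposition score is then kept and used.

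In the LOCF analysis, take the first 30-minute score as baseline only if the recorded dose times show that it preceded the first dose. Dose timing is already collected (protocol Appendix A, SAP 3.3).

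The cost is wording in two places and slightly more programming. No new data are needed, and the sample size and the SAP's primary test stay as they are.

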2.4. Planned Sample Size

A sample size of 230 subjects with ED visits provides 90% power to detect a 14-mm clinically significant reduction in pain scores for the patient-specific analgesic protocol versus the weight-based analgesic protocol with a 0.05 type I error using a horizontal Visual Analogue Scale 100 mm in length. This assumes the same standard deviation (SD) of 31 mm in pain score reductions in the two groups while accounting for 10%

missing data rate. (section 13)

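### At the planned 10% missing rate the best/worst imputation bounds are too wide to show whether the primary result is robust, and SAP 4.1 defines the worst case in two ways

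*SAP*

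**What the plan says.** SAP 4.1 tests the primary hypothesis on observed data, whatever the proportion missing. It then treats missing data in two branches.

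- **More than 5% of randomized patients missing.** Multiple imputation under MAR (1000 data sets) is a sensitivity analysis, judged supportive if it agrees with the primary analysis in direction and size. A further analysis, described only as potential, is the best/worst pair: "the worst scenario is to impute the pain score reduction to be zero for patient-specific analgesic protocol and observed maximum pain reduction" for the weight-based arm, with the reverse as the best scenario.
- **Fewer than 5% of patients missing.** Two analyses are planned. One is last observation carried forward. The other is "Worst case, assuming missing discharge pain scores are 0 in the weight-based arm and 100 in the patient-specific arm", with missing arrival scores set to the study mean.

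Protocol 13.8 concedes that MAR cannot be checked from the observed data and gives the same pair as its response: "We will consider the best and worst scenarios where the worst scenario is to impute the pain score reduction to be zero" in the patient-specific arm. It places multiple imputation in the primary analysis where the SAP makes it a sensitivity analysis. In neither document is the best/worst pair the primary test.

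The design expects appreciable missingness. SAP 4.1 sizes the trial for "pain score reductions in the two groups while accounting for 10% missing data rate", and protocol 13.7 reports 8% missing in the R34 pilot.

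**The concern.** A sensitivity analysis for missing data should tell the reader how far the missing outcomes must depart from MAR before the conclusion changes. Above 5% missing, the plan offers MAR itself and two extremes, with nothing between. If the extremes are so far apart that a sound 14 mm result nearly always loses significance under one, and a null result often gains it under the other, the pair says little about the result in hand.

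This matters here because protocol 13.8 names patients leaving before the final interview as a source of missing scores. Such missingness could plausibly relate to pain.

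Two further points affect how the pair would be read. The same SAP section gives two different rules for the worst case. The 5% threshold that chooses between them is counted on randomized patients in one branch and on patients, without qualification, in the other.

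**Working it through.** **Inputs from the documents**
- 230 patients with an ED visit, allocated 1:1, so 115 per arm; "A sample size of 230 subjects with ED visits provides 90% power to detect a 14-mm clinically significant reduction in pain scores" (SAP 2.4).
- Two-sided 0.05 (protocol 13.6); 100 mm scale and "the same standard deviation (SD) of 31 mm in pain score reductions in the two groups" (SAP 2.4).
- Mean reductions of 43 mm (patient-specific) and 29 mm (weight-based) in the pilot (protocol 13.7, Table 3).
- Missing rate m = 10%.

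**Assumptions**
- Observed maximum reduction M = 80 to 100 mm; the scale caps it at 100.
- The same missing rate in both arms, with data missing completely at random, so that the observed-data analysis is unbiased.

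**1. The plan's own figure.** Observed per arm: 230 × 0.9 / 2 = 103.5. SE = 31 × √(2/103.5) = 4.31 mm. Power = Φ(14/4.31 − 1.96) = Φ(1.29) = 90%. The stated power reproduces.

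**2. Expected estimates.** With true difference d:
- worst = (1 − m)d − mM
- best = (1 − m)d + mM
- gap = 2mM

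At m = 0.10 and d = 14, (1 − m)d = 12.6 mm. The gap is 16 to 20 mm for M = 80 to 100, wider than the 14 mm target.

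**3. Chance of significance under worst.** The variance in each arm is (1 − m)31² + m(1 − m)(arm mean − imputed value)², with 115 per arm.

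For M = 100: patient-specific 864.9 + 0.09 × 43² = 1031.3; weight-based 864.9 + 0.09 × 71² = 1318.6. SE = √(2349.9/115) = 4.52. Power = Φ(2.6/4.52 − 1.96) = 8%.

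| M (mm) | Worst (mm) | SE | 95% CI around expected value | Significant | Best (mm) |
|---|---|---|---|---|---|
| 80 | 4.6 | 4.30 | −3.8 to 13.0 | 19% | 20.6 |
| 90 | 3.6 | 4.40 | −5.0 to 12.2 | 13% | 21.6 |
| 100 | 2.6 | 4.52 | −6.3 to 11.5 | 8% | 22.6 |

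At the pilot's 8% missing, worst is 4.9 to 6.5 mm and significant in 19% to 33% of trials (M = 100 to 80).

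**4. No true effect.** With both means at 36 mm, best = mM = 8, 9 or 10 mm, with SE 4.19, 4.28 or 4.39. It is significant in favour of patient-specific care in 48%, 56% or 62% of trials for M = 80, 90 or 100.

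**5. Simulation check.** 3,000 trials per setting, scores bounded at 0 and 100, adjusted for arrival score (assumed mean 87, SD 9), 10% missing at random. A nominal 14 mm effect shrinks to 12.3 mm because of the bounds, and worst is then significant in 5% of trials. With the realised effect restored to 14 mm the figure is 11% to 12%, inside the 8% to 19% above.

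**6. The two worst-case rules.** For a patient with arrival score A:
- Below 5%: patient-specific reduction = A − 100, which is zero or negative; weight-based = A. The contrast is −100 mm.
- Above 5%: patient-specific = 0; weight-based = M. The contrast is −M.

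For the patient-specific arm the rule is therefore milder when more data are missing (0 instead of −15 mm for A = 85, for example). Negative reductions are plausible: a normal distribution with the pilot means and SDs puts 8% (43, SD 31) and 14% (29, SD 27) below zero. The net effect on the estimate is m(100 − M), which is 0 to 2 mm at 10% missing.

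**7. The trigger.** 10% of 230 is 23 patients. 23/460 randomized is exactly 5%, so read literally neither branch applies. 23/230 is 10%, and the first branch applies.

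**The case against.** Best/worst imputation is a recognised bounding method, and its limits are meant to widen as missingness grows. Wide limits at 10% report honestly how much the missing data could matter. The SAP also works to prevent missingness, through close monitoring and a site explanation at the first missing score. These points stand, and they make this an improvement to the plan and not the correction of an error in the primary analysis.

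A reader might infer four stronger things that the documents do not support.

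- **That the bounds ignore the data.** The observed difference keeps 90% of the weight at 10% missing, and M is itself observed. Only the gap between the bounds is free of the arm means.
- **That the worst scenario would overturn a true effect.** No success rule is attached to it; the wording on supportive results belongs to multiple imputation. The SAP's primary test uses observed data. The expected worst estimate still favours patient-specific care at 10%; its sign reverses only at about 12% (M = 100) to 15% (M = 80) missing.
- **That the mild zero rule causes the loss of significance.** A harsher rule would lose significance more often, so the two points are separate.
- **That the branch above 5% is certain to apply.** On the randomized denominator the planned rate falls exactly on the threshold, and the pilot's 8% (18 of 460) would be 4%.

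**Conclusion.** The concern holds in this limited form. At the planned missing rate the best/worst pair is too wide to inform: a true 14 mm difference becomes 2.6 to 4.6 mm, significant in about 8% to 19% of trials against 90% on observed data, and a null effect looks significant under best in about 48% to 62%. The consequence is a sensitivity analysis that will usually appear to fail, with no stated way to read it. The primary result is not at risk.

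The two worst-case definitions contradict each other whatever the simulation or assumptions, but cost only 0 to 2 mm at 10%. The unclear denominator decides which set of analyses is run.

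The sizes rest on M between 80 and 100 mm, equal missingness by arm and the pilot means. That the gap is 2mM needs only equal missingness.

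**What to change.** In SAP 4.1, and in protocol 13.8 to match:

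1. Add a delta-adjusted (tipping-point) analysis built on the 1000 imputations already planned. Worsen the imputed outcomes in the patient-specific arm in steps, for example 5 mm, and also vary both arms, until the 95% confidence interval includes zero. Report the tipping value and whether it is plausible.
2. If bounds are kept, use one definition in both branches (final score 100 in one arm and 0 in the other), and state that they are limits and do not decide robustness.
3. Define the 5% trigger on the modified ITT population in both branches, and say what happens at exactly 5%.

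The cost is a few sentences in each document and a few lines of code on imputations that will exist anyway. No data collection or sample size changes.
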